8.7. Data analysis

The detailed methodology for data analysis will be described in the Statistical Analysis Plan (SAP).

As a first step, extracted patients will be divided into two cohorts, primary prevention cohort and secondary prevention cohort based on the previous diagnosis of stroke. Clinical and demographic characteristics will be compared with two cohorts at baseline and on the index date (date of the initiation of warfarin and apixaban) and incidence rates of stroke/SE and major bleeding per 1,000 person-years will be calculated during follow-up period. In addition, interaction analysis will be conducted to investigate an interaction between OAC (warfarin/apixaban) and presence or absence of the previous episode of stroke.

- As a second step, only secondary prevention cohort will be used for further analyses as follows, Crude (before IPTW) patient characteristics are compared between warfarin and apixaban cohorts using appropriate methods (continuous variables: unpaired t-test or Mann-Whitney U-test, categorical variables: chi-square test)
- A propensity score is calculated based on multinomial logistic regressions in order to account for confounding effects and to ensure that patient characteristics are balanced between the warfarin cohort and apixaban cohort. An inverse probability of treatment weighting (IPTW) method using the calculated propensity score will be applied. To avoid sample size inflation and to ensure appropriate estimation of variances, s-IPTW (stabilized IPTW) is used here.
- Balanced (after IPTW) patient clinical and demographic characteristics are shown. Covariate balance between apixaban and warfarin cohorts after s-IPTW is assessed in terms of the standardized differences with a threshold of 0.1
- Kaplan Meier curves of balanced cohorts for each endpoint are drawn.
- Incidence rates of endpoints are calculated and shown per 1000 person-years.
- Hazard ratios with 95% confidence intervals will be calculated using a Cox proportional hazards regression model that incorporate only the index OACs as independent variables.

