**2.1. STUDY DESIGN**

*It is a non-interventional comparative observational study in which patients who meet the study criteria are selected and aggregated from the patients registered in the Medical Data Vision (MDV) database.*

In this study, analyses will be conducted in a 2-step manner. The first step is an epidemiological part and the number of patients of NVAF patients with a history of stroke (cerebral infarction, cardioembolic stroke, hemorrhagic stroke or TIA) or without a history of stroke in Japan, and clinical and demographic characteristics in each cohort will be investigated. In addition, incidence rate of stroke will be investigated in each cohort and presented as incidence rates per 1,000 person-years. Relative risk of stroke/SE and major bleeding will be estimated by using Logistic regression analysis and p for interaction between OAC (warfarin or apixaban) and a history of stroke (primary or secondary) will be calculated. In this first step, propensity score matching or IPTW will not be performed to balance the patient characteristics between cohorts.

[figure not shown]
PFIZER CONFIDENTIAL

In the second step, only the secondary prevention patients who are newly diagnosed with NVAF and initiate warfarin or apixaban for prevention of cardioembolic stroke. To balance the patient characteristics between warfarin and apixaban cohorts, an IPTW methods will be applied. Using the balanced warfarin cohort and apixaban cohort, incidence of events (stroke/SE or major bleeding) (per 1,000-year) will be calculated. Additionally, Cox proportional hazard analysis will be conducted to calculate hazard ratio + 95% confident interval.

PFIZER CONFIDENTIAL

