### 2.1.3. Treatment/cohort labels

Step-1

1. Primary prevention patients who are newly diagnosed with NVAF and initiated warfarin or apixaban (primary prevention cohort)
2. Secondary prevention patients who are newly diagnosed with NVAF and initiated warfarin or apixaban (secondary prevention cohort)

Step-2

1. Balanced Warfarin cohort of secondary prevention (warfarin cohort)
2. Balanced apixaban cohort of secondary prevention (apixaban cohort)

Patients will be assigned to each cohort based on the first prescription of oral anticoagulants after the diagnosis of NVAF (warfarin or apixaban). If the first oral anticoagulant prescribed was other than warfarin or apixaban or no oral anticoagulant was used, the patients will be excluded. Patient clinical and demographic characteristics will be balanced by using an IPTW method.

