## 2.2. STUDY OBJECTIVES

*The pivotal randomized clinical trial, ARISTOTLE study, and other RWE, in which medical and claims data have been retrospectively analyzed, have shown that the risks of incidence of stroke + systemic embolism and major bleeding in patients with NVAF treated with apixaban is equal to or lessor than those in patients treated with warfarin. As mentioned above, patients with NVAF and with a history of ischemic stroke (that is, in secondary prevention) could be at higher risk of recurrence and bleeding. Although neurologists generally use direct oral anticoagulants (DOAC) for secondary prevention, a significant portion of the patients in secondary prevention are still treated with warfarin in Japan. The*

results of randomized trials have been indicated that apixaban is superior to warfarin in reducing the risk of recurrence and/or bleeding with secondary prevention of stroke. However, there is no clear evidence in Japanese patients with secondary prevention of stroke. The research question of this study is whether apixaban is associated with lower risk of stroke (ischemic and hemorrhagic) and bleeding compared to warfarin in higher-risk secondary prevention patients as well.

The purposes of this study are 1) to characterize the primary and secondary prevention patients, 2) to calculate incidence rates of stroke/SE or major bleeding in each cohort and 3) to investigate for Japanese secondary prevention patients as RWE on the effectiveness and safety of apixaban compared to warfarin in patients NVAF.

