### 7.2.3. Summary of Analyses

All analysis other than patient characteristics will be conducted as a two-sided p-value less than 0.05.

Patient characteristics will be compared using standardized difference as a cut-off value of 0.1.

Outcome/items to be examined	Analysis Cohort	Supports Protocol Objective Number	Subgroup	Statistical Method	Covariates/Strata	Missing Data

PFIZER CONFIDENTIAL

Patients characteristics	Cohorts in Step 1 and Step 2		None	unpaired t-test or Mann-Whitney U-test, categorical variables: chi-square test		No imputation
The incidence rates of stroke/SE and major bleeding per 1,000 person-years	Cohorts in Step 1 and Step 2		None	1000 person-years	Refer to section 5.4	No imputation
Interaction analysis	Cohorts in Step 1 and Step 2		None	Cox proportional hazards regression model	Warfarin/apixaban, primary/secondary	No imputation
Incidence rate of a composite of recurrent stroke (ischemic and hemorrhagic)/SE (primary effectiveness analysis)	Balanced cohorts	Effectiveness 1	None	1000 person-years	Refer to section 5.4	No imputation
Incidence of cardiogenic cerebral embolism (secondary effectiveness endpoint)	Balanced cohorts	Effectiveness 1	None	1000 person-years	Refer to section 5.4	No imputation
Incidence of cerebral infarction (secondary effectiveness endpoint)	Balanced cohorts	Effectiveness 1	None	1000 person-years	Refer to section 5.4	No imputation
Incidence rate of major bleeding (primary safety endpoint)	Balanced cohorts	Safety 1	None	1000 person-years	Refer to section 5.4	No imputation
Incidence rate of intracranial hemorrhage (secondary safety endpoint)	Balanced cohorts	Safety 1	None	1000 person-years	Refer to section 5.4	No imputation
Incidence rate of gastrointestinal bleeding (secondary safety endpoint)	Balanced cohorts	Safety 1	None	1000 person-years	Refer to section 5.4	No imputation
Incidence of rate of intraocular bleeding (secondary safety endpoint)	Balanced cohorts	Safety 1	None	1000 person-years	Refer to section 5.4	No imputation
Time course of proportion of a composite of the incidence of recurrent stroke (ischemic and hemorrhagic)/SE -free NVAF patients treated with warfarin or apixaban	Balanced cohorts	Effectiveness 2	None	Kaplan Meier curves	Refer to section 5.4	No imputation

PFIZER CONFIDENTIAL

Time course of proportion recurrent cardiogenic cerebral embolism-free NVAF patients treated with warfarin or apixaban	Balanced cohorts	Effectivess 2	None	Kaplan Meier curves	Refer to section 5.4	No imputation

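### The Step 1 test of interaction between drug and stroke history is unadjusted for apixaban–warfarin differences within each prevention cohort, so it cannot separate effect modification from unequal confounding

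*SAP*

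**What the plan says.** SAP 2.1 divides the work into two steps. Step 1 takes primary and secondary prevention patients together. Its drug effects on the two main outcomes are to be expressed as relative risks from a logistic model. On effect modification the SAP says that a "p for interaction between OAC (warfarin or apixaban) and a history of stroke (primary or secondary) will be calculated". Later in that section comes the limit on adjustment: "In this first step, propensity score matching or IPTW will not be performed to balance the patient characteristics between cohorts".

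The interaction row in SAP 7.2.3 names a Cox model, gives the covariates as "Warfarin/apixaban, primary/secondary" and the analysis cohorts as "Cohorts in Step 1 and Step 2". The incidence, Kaplan-Meier and Cox outcome rows point to SAP 5.4 for covariates instead. SAP 7.2.3 also applies a two-sided 0.05 level to every analysis except patient characteristics.

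For Step 2, Protocol 8.7 says "only secondary prevention cohort will be used for further analyses as follows". SAP 2.1.3 likewise defines balanced cohorts for secondary prevention only. SAP 7.1.2 gives the reason for weighting: to deal with confounding between warfarin and apixaban patients. SAP 4.4 plans no subgroups. SAP 7.2.1 limits E-values to the primary effectiveness and safety analyses.

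**The concern.** An interaction between drug and stroke history compares two apixaban–warfarin contrasts, one per prevention cohort. Leaving the primary and secondary cohorts unbalanced against each other does no harm in a descriptive step. What matters for the interaction is whether apixaban and warfarin patients are comparable within each cohort. The SAP treats that comparability as something weighting must produce in Step 2, but does not seek it in Step 1.

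A crude contrast in each cohort carries its own confounding factor. If the two factors are equal, they cancel and the interaction is sound. If they differ, their ratio appears as effect modification. At stake is any statement in the report that the apixaban effect in secondary prevention resembles, or differs from, that in primary prevention. A reader is likely to set this p-value beside the randomized trial's interaction p of 0.71 cited in SAP 7.2.2, although only the latter comes from randomized groups.

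**Working it through.** **The plan's own figures.** SAP 7.2.2 gives sample sizes for the main comparison only; no power or effect size is stated for the interaction. The table reproduces with the Schoenfeld formula over 2 years. Example for HR 0.7 and 2.1%/year:
- Events = 4 × (1.960 + 0.842)² / (ln 0.7)² = 246.8, rounded up to 247.
- Control risk = 1 − 0.979² = 0.0416; apixaban risk = 1 − (1 − 0.0416)^0.7 = 0.0293.
- 247 / 0.0708 ≈ 3,487 per group, against 3,488 stated. All 12 cells agree within 4 patients.

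This confirms the table but does not bear on the interaction.

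**Can Step 2 supply an adjusted test?** No. A product of drug and stroke history needs both levels of history, and Step 2 has one. Naming both steps in the interaction row does not change that.

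**How bias enters.** Take one binary confounder that multiplies risk by g, with prevalence pA on apixaban and pW on warfarin. Within a cohort the crude contrast is multiplied by B = [1 + (g−1)pA] / [1 + (g−1)pW]. The crude interaction ratio equals the true ratio × B(secondary) / B(primary). Illustrations with no true interaction (all prevalences assumed):
- g = 2, 30% vs 40% in both cohorts: 0.929 / 0.929 = 1.00; the bias cancels.
- g = 1.5, secondary 25% vs 40%, primary 30% vs 30%: 1.125 / 1.20 = 0.94.
- g = 2, same prevalences: 1.25 / 1.40 = 0.89.
- g = 2, opposite directions (secondary 40% vs 30%, primary 20% vs 30%): 1.077 / 0.923 = 1.17.

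**Effect on the test.** Common inputs: 15,000 secondary patients (SAP 7.2.2 says more than this), split 1:1 (assumed), and HR 0.65 (SAP 7.2.2) in both cohorts. The false-positive rate is P(|Z| > 1.96) when Z is shifted by |ln 0.9| / SE, with |ln 0.9| = 0.105.

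*One year of follow-up, warfarin rate 2.1%/year.* Secondary events = 7,500 × 0.021 × (1 + 0.65) = 260. Let primary prevention have m times as many events (assumed). SE = √(4/260 + 4/(260m)).

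| m | SE | False-positive rate at ratio 0.9 |
|---|---|---|
| 1 | 0.175 | 9% |
| 3 | 0.143 | 11% |
| 5 | 0.136 | 12% |

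*Two years of full follow-up.* SE = √(sum of 1/events over the four groups). The primary rate of 1.2%/year and the primary cohort sizes are assumed.

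| Secondary rate | Primary patients | Events (sec. warfarin, sec. apixaban, prim. warfarin, prim. apixaban) | SE | False-positive rate at ratio 0.9 |
|---|---|---|---|---|
| 2.6%/year | 15,000 | 380, 249, 178, 116 | 0.144 | 11% |
| 2.1%/year | 30,000 | 308, 202, 356, 232 | 0.124 | 14% |
| 2.6%/year | 60,000 | 380, 249, 711, 464 | 0.101 | 18% |

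**Masking.** In the two-year scenarios a true ratio of 0.80 is detected with 34–60% power. An opposing bias of 1.2, slightly beyond the 1.17 illustration, makes the crude ratio 0.80 × 1.2 = 0.96, and power falls to 6–7%.

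**The case against.** Several counter-arguments stand and limit the point.

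- **Research question.** A reader might infer that the study's main conclusion rests on this p-value, because SAP 2.2 asks "whether apixaban is associated with lower risk of stroke (ischemic and hemorrhagic) and bleeding compared to warfarin in higher-risk secondary prevention patients as well". In context the closing words look back to the randomized trial and earlier real-world studies. The weighted Step 2 hazard ratio answers the question. No listed objective is a comparison of drug effect between prevention cohorts, the interaction row has no protocol objective entered, and no decision rule uses the result.
- **Wording.** A reader might take the Step 1 sentence as ruling out all adjustment. Taken literally it excludes matching and IPTW between cohorts, which in Step 1 are primary and secondary prevention; it does not exclude regression covariates. The reading of drug and cohort only comes from the SAP 7.2.3 row. That column is an imperfect guide: it sends the Step 2 Cox rows to SAP 5.4, while Protocol 8.7 puts only the index drug in those models. Still, nowhere does the text plan an adjusted interaction. Protocol Figures 1a and 1b were not available for this check.
- **Mechanism.** Differences in risk or antiplatelet use between primary and secondary patients do not by themselves bias the interaction. Drug-related imbalance, or its effect on risk, has to differ between cohorts, and the documents do not show that it does.
- **Size.** A reader might quote far larger error rates: a spurious ratio of 0.7 would give 53–75% in the one-year scenarios. With a risk-doubling confounder and a balanced primary cohort, that needs about 12% vs 60% prevalence by drug (1.12 / 1.60). A ratio of 0.8 needs about 20% vs 50% (1.20 / 1.50). These are extreme, and nothing in the documents supports them.

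The description of Step 1 as epidemiological, and the exploratory caveat in SAP 7.2, do not dispose of the point. The caveat concerns multiplicity and sub-endpoints, whereas this interaction concerns stroke/SE and major bleeding. An exploratory label does not remove bias.

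**Conclusion.** The point holds at moderate weight. The only planned test of effect modification by stroke history is crude with respect to drug choice, and it is sound only under equal confounding in the two cohorts, an assumption left unstated and unchecked. For a spurious ratio of 0.9 and no true interaction, the nominal 5% error becomes roughly 9–18%. That range depends on the assumed ratio, 1:1 drug split, follow-up, event rates and primary-cohort size; it shows sensitivity and does not predict the bias in this database. The finding is confined to the Step 1 interaction and statements built on it. It gives no ground for doubting the weighted Step 2 primary analyses.

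**What to change.** For the interaction analysis only:
1. Fit the drug propensity score separately in the primary and secondary prevention cohorts. The primary-cohort list omits the stroke-specific items of SAP 7.1.2, such as type of most recent stroke and mRS, JCS and ADL at the stroke admission.
2. Apply stabilized weights within each cohort and report apixaban–warfarin balance in each.
3. Fit drug, stroke history and their product in a weighted Cox model with robust variance. Report the weighted hazard ratio per cohort with the interaction p-value.
4. Keep Step 1 characteristics and crude incidence rates unweighted. Label any crude interaction as unadjusted and descriptive.
5. Reconcile SAP 2.1 (logistic) with SAP 7.2.3 (Cox), and correct the cohort entry for that row. Logistic regression would also ignore the unequal follow-up created by the censoring rules in Protocol 8.1.1.7.

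The cost is one extra propensity model, derivation of its covariates for the primary cohort (the documents do not say these are already planned there), and a somewhat wider interval for the interaction. Residual confounding remains, because laboratory values are unavailable (Protocol 8.9) and the two covariate lists differ. If the extra model is not wanted, the labelling in item 4 is the minimum.

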### 2.1.1. Study population

*NVAF patients in secondary prevention of ischemic stroke who are treated with warfarin or apixaban, registered in the MDV database (2008-2021).*

In the preliminary survey the number of patients will be estimated as follows (this was a rough estimation)

- *The number of estimated patients;*
- *All registered patients: approximately 38 millions (2008-2021)*
- *Patients with ischemic stroke: 1.2 millions*
- *Patients with TIA: 98,887*
- *Patients with atrial fibrillation: 1.3 millions*
- *NVAF patients with a history of ischemic stroke: 226,000*
- *NVAF patients on warfarin: 251,000*
- *NVAF patients on apixaban: 237,000*
- *The number of patients who experienced recurrent ischemic stroke on warfarin or apixaban: unknown*

### 2.1.2. Data source

#### **Medical Data Vision database**

*De-identified health claim data from 458 acute-care hospitals across Japan (as of Dec.22, 2021) available from the MDV (Tokyo, Japan, MDV) database. In brief, the MDV database comprises administrative data pertaining to approximately 38 million individuals managed in the inpatient and outpatient settings. Each patient is associated with a specific identifier (ID) to which all inpatient and outpatient data are linked.*

### 2.1.3. Treatment/cohort labels

Step-1

1. Primary prevention patients who are newly diagnosed with NVAF and initiated warfarin or apixaban (primary prevention cohort)
2. Secondary prevention patients who are newly diagnosed with NVAF and initiated warfarin or apixaban (secondary prevention cohort)

Step-2

1. Balanced Warfarin cohort of secondary prevention (warfarin cohort)
2. Balanced apixaban cohort of secondary prevention (apixaban cohort)

Patients will be assigned to each cohort based on the first prescription of oral anticoagulants after the diagnosis of NVAF (warfarin or apixaban). If the first oral anticoagulant prescribed was other than warfarin or apixaban or no oral anticoagulant was used, the patients will be excluded. Patient clinical and demographic characteristics will be balanced by using an IPTW method.

## 2.2. STUDY OBJECTIVES

*The pivotal randomized clinical trial, ARISTOTLE study, and other RWE, in which medical and claims data have been retrospectively analyzed, have shown that the risks of incidence of stroke + systemic embolism and major bleeding in patients with NVAF treated with apixaban is equal to or lessor than those in patients treated with warfarin. As mentioned above, patients with NVAF and with a history of ischemic stroke (that is, in secondary prevention) could be at higher risk of recurrence and bleeding. Although neurologists generally use direct oral anticoagulants (DOAC) for secondary prevention, a significant portion of the patients in secondary prevention are still treated with warfarin in Japan. The*

results of randomized trials have been indicated that apixaban is superior to warfarin in reducing the risk of recurrence and/or bleeding with secondary prevention of stroke. However, there is no clear evidence in Japanese patients with secondary prevention of stroke. The research question of this study is whether apixaban is associated with lower risk of stroke (ischemic and hemorrhagic) and bleeding compared to warfarin in higher-risk secondary prevention patients as well.

The purposes of this study are 1) to characterize the primary and secondary prevention patients, 2) to calculate incidence rates of stroke/SE or major bleeding in each cohort and 3) to investigate for Japanese secondary prevention patients as RWE on the effectiveness and safety of apixaban compared to warfarin in patients NVAF.

### 3. HYPOTHESES AND DECISION RULES

#### 3.1. STATISTICAL HYPOTHESES

Not applicable

#### 3.2. STATISTICAL DECISION RULES

When the effect of factors in an analysis is statistically evaluated, the alpha level of 0.05 will be referred.

### 4. ANALYSIS SETS/POPULATIONS

#### 4.1. FULL ANALYSIS SET

##### 4.1.1. Inclusion criteria

*Patients must meet all the following selection criteria*

1. *Patients registered in the MDV database 2008 through 2021.*
2. *Patients newly diagnosed with non-valvular atrial fibrillation*
3. *Patients who started anticoagulation treatment with either warfarin or apixaban after diagnosis of NVAF*
4. *Age 20 years or older on the index date*
5. *Patients who have a history\* of stroke (cerebral infarction, cardioembolic stroke, or hemorrhagic stroke) or TIA before the index date are inclusion criteria only for secondary prevention cohort, otherwise patients will be included in the primary prevention cohort.*

\* A history of stroke is checked as far back as possible from the INDEX DATE to see if there is a history of stroke. That is, the period is from the date each patient first appeared in the MDV database to the day before the index date.

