#### **4.1.2. Exclusion criteria**

*Patients who meet the following exclusion criteria will be excluded from this study*

1. *Patients with a diagnosis of valvular AF (standard disease code: 8846941), postoperative AF (8847772), AF associated with mechanical valve malfunction (T82.0), mechanical complication of heart valve prosthesis (T82.0), or rheumatic AF (I05-I09) during the baseline period\*\*.*
2. *Patients with a diagnosis of VTE during the baseline period*
3. *Patients who are prescribed any anticoagulant during the baseline period.*
4. *Patients who are prescribed anticoagulants other than warfarin and apixaban on the index date*
5. *Patients who were hospitalized for more than 6 months (including index date) regardless of reason for hospitalization.*

*\*\*: maximally 6 months prior to the index date. If sufficient patient information is available for the analysis, patients who cannot have a 6-month baseline period will be included in the analysis.*

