  - Coronary heart disease in baseline
  - Peripheral arterial disorder in baseline
  - History of myocardial infarction
  - Hyperthyroidism or thyrotoxicosis in baseline
  - Diabetes in baseline
  - Liver diseases in baseline
  - Diabetes mellitus diagnosis in baseline
  - Cancer diagnosis in baseline
  - Dementia in baseline
  - Renal diseases in baseline
  - Gastrointestinal ulcer in baseline

PFIZER CONFIDENTIAL

- History of bleeding
- Medicines
  - Treated with antiplatelet drug in baseline
  - Treated with NSAIDs in baseline
  - Treated with anti-hypertensives in baseline
  - Treated with anti-arrhythmics in baseline
  - Treated with beta-blockers in baseline
  - Treated with heparins in baseline
- Others
  - Cardioversion
  - Cardiac ablation

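### Prior stroke is searched back to each patient's first database record with no minimum record length, so some true secondary-prevention patients will be counted as primary prevention in Step 1

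*SAP*

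**What the plan says.** The footnote to SAP 4.1.1 sets the rule for stroke history: "A history of stroke is checked as far back as possible from the INDEX DATE to see if there is a history of stroke". It then defines the window: "the period is from the date each patient first appeared in the MDV database to the day before the index date". Inclusion criterion 1 gives the calendar span as "Patients registered in the MDV database 2008 through 2021", and SAP 2.1.2 describes the database "as of Dec.22, 2021". For patients in whom no stroke or TIA is found, criterion 5 says "otherwise patients will be included in the primary prevention cohort".

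No minimum record length is set. SAP 4.1.2 relaxes even the baseline window: where the available information is judged sufficient, "patients who cannot have a 6-month baseline period will be included in the analysis".

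Step 1 (SAP 2.1) uses this split to report the number of patients with and without stroke history, their characteristics and their incidence rates. It also plans that "p for interaction between OAC (warfarin or apixaban) and a history of stroke (primary or secondary) will be calculated". Step 1 has no matching or weighting. The only sensitivity analysis (SAP 7.2.1) is the E-value for the primary effectiveness and safety analyses. Protocol 8.9, limitation 3, deals with records lost after registration and says nothing about history that predates the first record.

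**The concern.** The rule treats the absence of a record as the absence of a stroke. A patient whose stroke was treated elsewhere, or before the hospital's data begin, is labelled primary prevention unless the stroke is coded again between the first MDV record and index. How often this happens depends on how much record exists before index. That varies from patient to patient and is neither fixed, bounded below nor reported.

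Two of the three purposes in SAP 2.2 rest on this split: characterising primary and secondary prevention patients, and giving event rates in each cohort. Misfiled patients shrink the secondary cohort, raise the event rate in the primary cohort if their risk is higher, and blur the contrast that the interaction test examines.

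The effect on Step 2 is different. Patients whose stroke is missed drop out of the secondary cohort; they are not mixed into either drug arm.

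**Working it through.** The documents give no look-back length, so there is no figure of theirs to reproduce. All results below are illustrations.

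**1. Longest possible look-back.** Index date minus 1 January 2008 (assumed earliest record):

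| Index date | Longest look-back (years) |
|---|---|
| 31 Dec 2008 | 1.0 |
| 31 Dec 2014 | 7.0 |
| 1 Jan 2021 | 13.0 |
| 22 Dec 2021 | 13.97 |

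The shortest possible look-back is close to 0 in every year, because the clock starts at the patient's own first record.

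**2. Share of prior strokes detected.** Assume time since stroke is exponential with mean μ years and that a stroke is seen only if it falls inside the look-back. With M the longest look-back at mid-year (1.5 years in 2009, 13.5 in 2021):

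- all records start in 2008: 1 − exp(−M/μ)
- first record uniform between 2008 and index: 1 − (μ/M)(1 − exp(−M/μ))
- everyone has exactly 1 year of record: 1 − exp(−1/μ)

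| Record pattern | μ = 3: 2009 / 2021 | μ = 5: 2009 / 2021 |
|---|---|---|
| All from 2008 | 39% / 99% | 26% / 93% |
| Uniform to index | 21% / 78% | 14% / 65% |
| 1 year for all | 28% / 28% | 18% / 18% |

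The third row has no calendar trend but heavy under-detection.

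**3. Range of the missed share m.** Assume 30-60% of strokes lie within 3 months of index and the rest are exponential with mean 4-8 years. Patients whose index date would precede their first record cannot be in the data and are left out.

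- Low end: records from 2008, index dates uniform 2015-2021 (look-back 7-14 years), 60% recent, mean 4 years. m = 0.4 × 4 × (exp(−7/4) − exp(−14/4))/7 = 0.4 × 0.082 = 0.03.
- High end: look-back exponential with mean 2 years, 30% recent, mean 8 years. m = 0.7 × 8/(8 + 2) + 0.3 × 0.06 = 0.58. Cutting look-back off at 2008 brings this to about 0.60.

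So m is roughly 3-60%.

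**4. Effect on Step 1.** Take a true stroke-history share of 17.4% (226,000/1.3 million, SAP 2.1.1) and warfarin rates of 1.2 and 2.6 %/year for true primary and secondary patients. Both are assumptions. The 17.4% is itself a recorded figure, for ischemic stroke among all AF patients. SAP 7.2.2 lists the two rates as alternative control rates and does not assign 1.2 to primary prevention.

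- Observed secondary share = 0.174 × (1 − m): 16.9% at m = 0.03, 7.0% at m = 0.60.
- Share of the primary cohort that is truly secondary: c = 0.174m/(1 − 0.174(1 − m)): 0.6% at m = 0.03, 11.2% at m = 0.60.
- Primary-cohort rate = 1.2 × (1 + c(2.6/1.2 − 1)): 1.21 to 1.36 %/year, that is 12.1 to 13.6 per 1,000 person-years against 12.

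**5. Difference between drugs.** This needs one more assumption: warfarin starts uniform over 2008-2021, apixaban starts later. The observed primary-cohort hazard ratio is 0.65 × (1 + 1.167c_A)/(1 + 1.167c_W), with the 0.65 of SAP 7.2.2 as truth. Take records from 2008, 30% recent strokes, mean 8 years and apixaban from 2015:

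- m_W = 0.7 × 8 × (1 − exp(−14/8))/14 + 0.3 × 0.125/14 = 0.333, so c_W = 0.0656
- m_A = 0.7 × 8 × (exp(−7/8) − exp(−14/8))/7 = 0.194, so c_A = 0.0394
- hazard ratio = 0.65 × 1.046/1.076 = 0.63

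With the 2-year exponential look-back the result is 0.647-0.648. With the same index-date distribution in both drugs, c_A = c_W and it is 0.65 exactly.

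**The case against.** Using all available history finds the most strokes, and a short fixed window would refile patients with older recorded strokes as primary. That stands, and it is why the main definition should stay.

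Old strokes are often coded again at later visits, so counting a stroke as missed whenever it predates the record is a worst case. That also stands. The code list is in a spreadsheet that cannot be read here, so the softening cannot be sized.

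Step 1 is the descriptive part of the study and carries neither primary endpoint. This limits the weight of the point, but does not remove it, since the Step 1 results are stated purposes of the study.

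A reader might go further in three ways that the documents do not support:

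- *Prior stroke is missed more often in earlier starters.* Only the ceiling on look-back rises with calendar year. A 2021 starter first seen in 2021 also has a short record. Whether detection improves over time depends on registration dates that are not given.
- *The comparison of drugs in the primary cohort is materially biased towards apixaban.* No start dates by drug are given, and under assumptions that favour the effect the shift is from 0.65 to about 0.63.
- *The Step 2 major-bleeding hazard ratio is biased through "History of bleeding" in the propensity list.* The open-ended search is defined for stroke only. The missing baseline label does not show that bleeding is searched the same way: hypertension also lacks it in SAP 7.1.2, yet SAP 5.4 calls it a baseline characteristic. A bias would further need assumed drug timing, prevalence and rate ratio.

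**Conclusion.** The point holds for Step 1. The classification rule has no minimum record length, defaults to primary prevention, and is not covered by any planned sensitivity analysis or stated limitation. Enforcing the 180-day baseline of Protocol 8.1.1.6 would not settle it, since searches would still run from about 0.5 to 14 years.

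That some secondary patients are misfiled needs no assumption about when each drug was started. The extent does rest on assumptions: roughly 3-60% of true secondary patients missed, depending on record starts and stroke timing, and fewer with re-coding. The width of that range is itself a reason to report look-back length. Any difference between drugs is conditional on later apixaban starts and small (about 0.63-0.65 against 0.65). There is no demonstrated effect on the Step 2 primary analyses.

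**What to change.** In SAP 4.1.1, 2.1 and 7.2.1:

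1. Keep the all-available search as the main definition of stroke history.
2. Derive look-back length (first MDV record to index date) for every patient and report its distribution by cohort, drug and index year.
3. Repeat the Step 1 counts, characteristics, incidence rates and interaction with a stated minimum record length before a patient without recorded stroke is labelled primary prevention, for example 1 year, with 3 years as a second cut. Exclude shorter-record patients without recorded stroke and refile no one. Show the excluded patients as a separate count, because removing them from one side only raises the apparent secondary share.
4. Add to the limitations that strokes before the first record may be unseen.

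The cost is SAP wording, one variable from dates the plan already uses, and one set of tables. The repeat loses short-record patients, and it reduces misclassification without ending it: under the exponential illustration with mean 5 years, a record of exactly 3 years still detects only 1 − exp(−3/5) = 45% of prior strokes, against 18% with 1 year.
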